7 DATA ANALYSIS

A detailed statistical analysis plan will be developed prior to completion of the statistical analysis. The analysis plan will provide a full description of the variables of interest, statistical methods (including management of missing data, statistical adjustment, management of confounding factors and interactions), subgroup definitions and sensitivity analyses.

7.1 PRIMARY ANALYSIS

A conditional logistic regression model will be fitted with the logarithm of anti-malarial antibody levels to Circum Sporozoite Protein (CSP) as the independent variable. The p-value for the test of no association between anti-malarial antibody levels and case/control will be presented.

7.2 SECONDARY ANALYSIS

- Compare anti-malarial antibody levels against other antigens between severe and non-severe COVID-19 cases:
 - A model similar to that for the primary objective is fitted with the respective anti-malarial antibody levels as the independent variable.
- Comparing the cellular response against malaria between severe and non-severe COVID-19 cases:
 - A conditional logistic regression model will be fitted with cellular response against malaria as the independent variable.
- Compare the proportions of acute malaria infection between severe and non-severe cases of COVID-19 using the Thick Gout (TG) and Rapid Diagnostic Test (RDT).
 - A conditional logistic regression model will be fitted with the proportions of acute malaria infection as the independent variable.
- Describe the clinical characteristics and clinical status of severe and non-severe cases of COVID-19 with and without malaria (former exposure or active infection):
 - Medians with quartiles or numbers and proportions will be presented.
- Evaluate the modulatory impact of existing antimalarial immunity on the strength of humoral and cellular immune responses to SARS-COV-2 in severe and non-severe cases of COVID-19
 - A conditional logistic regression model will be fitted with the SARS-COV-2 specific cellular immune response as the independent variable.

7.3 SUBGROUP ANALYSIS

No subgroup analysis will be performed.

7.4 MULTIPLICITY AND MISSING DATA

As this is a study with a single primary objective, no multiplicity adjustment is necessary. The management of missing data will be specified in the statistical analysis plan.

8 ETHICAL CONSIDERATIONS

8.1 ETHICAL (AND REGULATORY) REVIEW

The investigators would be committed to conducting the study in accordance with the principles of the Declaration of Helsinki. Prior to carrying out the study, official approval would be obtained from the ethics committee; the study protocol would be submitted for approval to the ITM's institutional review, to the ethics committee of Belgium's Antwerp University Hospital, and to the national ethics committee of the DRC's Ministry of Public Health. Authorization will also be sought from the relevant health zones before the study begins.

8.2 PROTOCOL CHANGES

Once the final study protocol has been issued and signed by the authorized signatories, it cannot be modified informally. Amendments to the protocol have the same legal status and must go through the appropriate steps before being implemented. Any substantial modification must be approved by all the bodies and the Ethics Committee (EC) that approved the original protocol, before being implemented, unless it is due to participant safety concerns (in which case immediate implementation may be necessary for participant protection). If changes to the protocol or an amendment are requested by a local EC during the review process, they must be discussed and agreed with the sponsor prior to any resubmission incorporating these changes.

8.3 OBTAINING INFORMED CONSENT

Before starting the study, the investigator assigned to the site (CTCO or ZS) will obtain informed consent from the participants; this will consist of asking for their opinion and explaining the purpose, objectives, rights of the participants and responsibilities of the investigation team. Consent will ensure that each participant understands all procedures. Participants will receive clear explanations of all possible techniques that will be used by their samples.

The informed consent form will be translated into the local language (Lingala) at the language service of the University of Kinshasa. The informed consent procedure will be conducted in the patients' mother tongue or preferred language by a qualified person, indicated by the principal investigator.

Patients will have sufficient time to ask questions and make a free decision. If the person is willing to participate, he or she will be asked to sign the consent form. If the participant cannot read and/or write, an impartial witness should be present during the informed

PROTOCOL: MALARIA AS A PROTECTIVE FACTOR AGAINST SEVERE COVID-19 IN THE DEMOCRATIC REPUBLIC OF CONGO

consent discussion. After the written informed consent form has been read and explained to the participant, and after he/she has orally consented to participate in the study and provided his/her fingerprint, the witness should complete the participant's name and add the date of the fingerprint, then personally sign and date the consent form. By signing the consent form, the witness attests that the information contained in the consent form and all other written information has been accurately explained to the participant, that the participant has apparently understood it, and that the participant has freely given consent.

The person obtaining informed consent will be asked to sign and date a written confirmation that he/she has been sufficiently informed about all relevant aspects of this study and confirms that he/she has freely and voluntarily consented to participate in the study.

For patients who are unable to give consent due to their clinical condition, consent will be obtained from a legally acceptable representative. As soon as the patient is able to give consent, the consent procedure will be repeated and the patient will be given the opportunity to confirm/refuse participation.

8.4 PRIVACY

Individual medical information collected in this study will remain confidential. Members of the study team are bound by professional secrecy. Individual data will be made available to physicians in charge of patients upon request to the investigators. Disclosure of this information to third parties is strictly forbidden.

Electronic files will not contain any data that could identify the participant (e.g. surname, first name, full date of birth, telephone number). Each study participant will be assigned a unique identification code (ID). On all study documents or files, study participants will be identified by the participant's ID code.

A correspondence list will establish the link between the participant ID and the participant's personal data so that examination results can be used for patient care. This list containing personal data and other documents containing participants' names or signatures (e.g. informed consent) will be kept separate from other study documents. All study documents will be kept in a secure, locked location, with access limited to the site principal investigator and authorized personnel.

Access to all paper documents and electronic files required for data management and study follow-up will be restricted to authorized personnel at international, regional and local levels. Study computers and CRF files will only be accessible via a login with a personal username

and password. A list of authorized CRF and database users will be kept at ITM and updated throughout the study.

8.5 RISKS AND BENEFITS

The direct benefit of the study is that each participant will receive a free malaria test with an additional examination, namely a blood sample. This will be the only additional examination compared to basic care. In addition, as compensation for their time, the controls will receive masks and soap to limit the spread of the virus in their environment.

Participation in the study will also benefit the community; it will contribute to the acquisition of knowledge about COVID-19, and the information it will generate will enable researchers or the response team to improve management. The only additional procedure specific to the study will be follow-up visits for controls: telephone contacts, or for patients for whom this is not possible: a physical visit either at the study site or at home.

The greatest risk for participants is a potential breach of confidentiality, for which all measures will be in place to limit this as much as possible (by de-identification). The sting may also cause a little pain and swelling at the sampling site, but this is temporary. In the event of significant risk, as assessed by the clinician, the sample will not be taken and the patient will be excluded (see inclusion/exclusion criteria).

8.6 SAMPLE STORAGE

The samples collected can be stored for a maximum of 20 years, so that they can be used for further research into COVID-19 immunization in line with future scientific discoveries. These samples will be stored and registered at INRB's bio-banking facilities in Kinshasa. Subjects will be asked to indicate on the informed consent form whether or not they agree to long-term storage.

The decision whether or not to use the samples for future research will be made by the study investigators in consultation with, and only after receiving approval from, the Institutional Review Board (IRB) and ethics committees.

8.7 INSURANCE

The coordinator of this study, ITM, has obtained study (no-fault) insurance to cover any injury, damage or loss to study participants caused directly or indirectly by their participation in the study. Information about the insurance is not specified in the Informed Consent Form for this study due to the expressed concern about unreasonable claims for compensation. Furthermore, we do not anticipate any specific physical injuries or mental health problems as a result of participation in this observational study.

8.8 MONITORING AND QUALITY CONTROL

Detailed SOPs will be developed to cover all laboratory processes, from sample collection to shipping, analysis and storage. Immunological and parasitological tests will be carried out by qualified laboratory technicians. The INRB and ITM PIs will be responsible for ensuring that all study-specific analyses are carried out in accordance with Good Clinical Laboratory Practice (GC(L)P) guidelines, study-specific Standard Operating Procedures (SOPs), and the internal/external quality control systems of the respective tests. During visits by the ITM research team, compliance with the protocol and GC(L)P will be monitored, including data management and documentation.

9 DISSEMINATION OF RESULTS AND INTELLECTUAL PROPERTY

All study documents are provided by the principal investigators to the investigators and their designated personnel in strict confidence. None of these documents may be disclosed to any party not directly involved in the study, without the written authorization of the principal investigators.

Once the results are considered final, arrangements will be made to communicate them to the Kinshasa community in the most appropriate way, with the active participation of the health authorities. Oral communications and written publications will mention the name of the sponsor and the names of all partners and researchers involved.

10 CALENDAR

N°	Tasks	Managers	Mars 21	April 21	Ma y 21	Jun e 21	July 21	Augu st 21	Sept 21	Oct 21	Nov 21	Dec 21	Janv 22	Feb 22	Marc h 22
1	Drafting the protocol	- Principal investigator - Scientific Committee													
2	Submission and approval Ethics Committee	- Investigator - Developer													
3	Preliminary steps : - Contact with political and administrative authorities	- Investigator - Supervisor - Scientific Committee													

PROTOCOL: MALARIA AS A PROTECTIVE FACTOR AGAINST SEVERE COVID-19 IN THE DEMOCRATIC REPUBLIC OF CONGO

	
 - Survey tool finalized - Interviewer training 													
4	Collecting data	Investigators												
5	Laboratory analysis of samples	Survey team												
6	Data capture and analysis	
 - Project management/Monitoring - Data management 												
7	Summary of results	Scientific Committee												

1. INTRODUCTION

This Statistical Analysis Plan (SAP) provides a detailed and comprehensive description of the main pre-planned analyses for the study "Malaria as a protective factor against severe forms of COVID-19 in DRC". The high prevalence of malaria in sub-Saharan Africa may play a role, according to some studies, in a possible protection against the severity of COVID-19 in endemic areas. However, the scientific evidence for the physiological role of this "induced" immunity is not established. We wish to conduct this study to elucidate this hypothesis. Details on the conduct of the study are described in the protocol.

These planned analyses will be carried out by statisticians from the Clinical Research Centre (CRC/INRB) and the Clinical Trials Unit of the Institute of Tropical Medicine (CTU ITM, Antwerp). The results of the analysis will be described in a statistical analysis report, which will serve as the basis for major research publications. This document describes the statistical methods for the primary and secondary objectives of the study as defined by the protocol. Additional analyses may be performed but are not covered by the current analysis plan.

This analysis plan will be finalised and approved before the database of the first analyses is locked. Major changes in the statistical methodology used for the main and pre-planned analyses of this SAP require a detailed description and justification in the Statistical Analysis Report (SAR). The dataset, programmes and final results are archived in accordance with Good Clinical Practice guidelines (ICH E9).

2. STUDY DESIGN AND OBJECTIVES

2.1. DESIGN

An observational, multi-centre, matched case-control study. The study will compare the quality of malaria immunity in severe and non-severe cases of COVID-19. The study will be conducted in four Treatment Centres (CTCo) to recruit severe cases (cases). Controls will be recruited at the Health Zone (HZ) level on the basis of the same characteristics as the cases, taking into account age (upper and lower 10 years), sex and HZ of origin.

2.2. OBJECTIVES

THE MAIN OBJECTIVE:

is to investigate whether the immunity conferred by Plasmodium protects against severe forms of COVID-19. This will be done by comparing Plasmodium antibody levels in severe and non-severe COVID-19 cases.

SECONDARY OBJECTIVES

They are :

- Comparing the cellular response against malaria between severe and non-severe COVID-19 cases
- To compare the proportions of acute malaria infection between severe and non-severe cases of COVID-19 using the Thick Gauge (TG) and Rapid Diagnostic Test (RDT)
- Describe the clinical characteristics and status of severe and non-severe cases of COVID-19 with and without malaria exposure
- To assess the modulating impact of existing antimalarial immunity on the strength of humoral and cellular immune responses to SARS-COV-2 in severe and non-severe cases of COVID-19
- Compare the SARS-COV-2 specific cellular immune response between severe and non-severe cases
- Assessing the modulatory impact of antimalarial immunity on induced immunity using specific antiviral receptor stimulations of the innate immune system

3. HYPOTHESES OF THE STUDY

Anti-malarial immunity would play a protective role against severe forms of COVID-19.

4. VARIABLES OF INTEREST**4.1. PRIMARY VARIABLES OF INTEREST :**

The primary variable of interest in the study is the level of anti-malarial antibodies in severe and non-severe COVID-19 cases. This level will be assessed by measuring the concentration of IgG against Circum Sporozoite Protein (CSP) using the Luminex-MAGPIX.

4.2. SECONDARY VARIABLES OF INTEREST :

- Anti-malarial IgG antibody levels against other antigens: AMAI, CSPM, GLURP, *Pf/RESA55*, as well as IgM antibodies

- Cellular response against malaria between severe and non-severe COVID-19 cases, measured by IFN-γ ELISPOT
- The proportions of acute malaria infection between severe and non-severe cases of COVID-19 using the Thick Gauge (TG) and Rapid Diagnostic Test (RDT). Indicator variables will be used for a positive RDT result, for a positive EW result and for a positive result with both tests
- Clinical features :
 - Duration of symptoms
 - Type of symptoms
 - Size
 - Weight
 - Blood pressure
 - Heart Rate
 - Respiratory Rate (RR)
 - Temperature (T°)
 - Free Oxygen Saturation (SaO2)
 - Splenomegaly

and clinical status of severe and non-severe cases of COVID-19 with and without malaria.

The clinical status of COVID-19 only controls is assessed by the WHO 10-point clinical progression score at 7^{ème} days of follow-up¹ :

Patient's condition	Description	Score
Not infected	Not infected; no viral RNA detected	0
Ambulatory: illness benign	Asymptomatic; viral RNA detected	1
	Symptomatic; independent patient	2
	Symptomatic; need for assistance	3
Hospitalized: moderate illness	Hospitalized; no oxygen therapy	4
	Inpatient; oxygen therapy by mask or nasal route	5
Hospitalized: illness severe	Inpatient; high flow oxygen therapy	6
	Intubation and mechanical ventilation, $pO2/FiO2 \geq 150$ or $SpO2/FiO2 \geq 200$	7
	Mechanical ventilation $pO2/FIO2 < 150$ ($SpO2/FiO2 < 200$) or vasopressors	8

	Mechanical ventilation pO ₂ /FiO ₂ <150 and vasopressors, dialysis, or ECMO	9
Deaths	Deaths	10

- SARS-COV-2 specific cellular and humoral immune response of severe and non-severe cases, measured by Luminex and ELISPOT.
- Induced immunity: Levels of antiviral cytokine release, measured by ELISA and flow cytometry, of peripheral blood monocytes (PBMC) from controls and patients with acute malaria infection (according to GE and RDT).

4.3. EXPLORATORY VARIABLES OF INTEREST :

- The proportion of patients infected with urinary and intestinal parasites.

5. POPULATION OF THE STUDY

This case-control study will be conducted in the Republic of Congo in the city of Kinshasa, the epicentre of COVID-19. Kinshasa is a malaria endemic area, the distribution of malaria prevalence is lower in urban areas compared to peri-urban areas. In fact, the city of Kinshasa is structured in four health districts and sixteen hospitals, distributed in the thirty-five health zones for the management of COVID-19.

The study consists of cases and controls: For each case, a control will be recruited.

5.1. DESCRIPTION OF CASES

The cases will be severe COVID-19 cases, which will consist of inpatients recruited from COVID-19 Treatment Centres (CTCOs).

5.2. DESCRIPTION OF

Controls will consist of asymptomatic or symptomatic cases without signs of severity. For each case, a control will be recruited after being matched in terms of age (plus or minus 10 years), gender and

Health Zone of origin. The time to recruit a control is up to 10 weeks after case recruitment.

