5.1.4 RECRUITING WITNESSES

For each case, two controls will be recruited in the Health Zone from which the severe cases originated. The Health Zone nurse assigned to the COVID-19 response and the investigator assigned to the site will record the witness information in the register of RT-PCR-positive cases for COVID-19.

The first two controls on the linear list with a COVID-19 RT-PCR test result of 72 hours or less and with the same characteristics will be contacted and invited to take part in the study. If participation is refused, the next person on the list will be taken. Controls must be matched to the case on the basis of the following concordance criteria:

- Age: +/- 5 years relative to case age
- Gender: same as case
- Place of origin: same health zone as the case

During the follow-up home visit planned by the ZS for the non-severe COVID19 patient, the investigator will accompany the ZS nurse supervisor, and the study will thus be introduced to the patient. Once informed consent has been obtained, the questionnaire and blood sample will be taken during the same visit. In compensation for their time, the controls will receive masks and soap to limit the spread of the virus in their environment.

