5.2 PROCEDURES

5.2.1 OVERVIEW OF STUDY PROCEDURES

Using the CRF, the investigator will interview both conscious cases and witnesses. For cases who are unconscious or unable to communicate, the medical file will serve as a source of information. Blood samples for cases and controls will be taken on D1 of the study.

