6.2. ANALYSIS POPULATION SECONDARY

Only participants who did not violate any major criteria will be included in the secondary analysis (see Table 1).

Table 1:Protocol violationsclassified as minor or major

Violation of the	Minor/major violation	Comments
Protocol Inclusion		
For CAS Criteria		
1. At least 18 years of age	Major	
2. Having an SARS-CoV infection confirmed by RT-PCR or rapid antigen test within 72 hours of inclusion.	Major	
3. Have given their informed consent or that of their guardian/ representative to participate in the study.	Major	
4. Clinical signs of pneumonia: fever, cough, dyspnea or crepitations and (Respiratory rate > 30 cycles/min or severe respiratory distress or SpO2 < 90% on room air)	Major	
5. Being admitted to a care unit for COVID-19	Major	
6. Reside in the health zone for at least 6 months	Minor	

For WITNESSES

1. Be at least 18 years old	Major
2. Have a PCR or antigenic test confirmed SARS-CoV- 2 infection within 72 hours prior to inclusion.	Major
3. Have given informed consent to participate in the study	Major
4. Be asymptomatic or symptomatic, but without any signs of severe pneumonia	Major
5. Not to be admitted to a care unit for COVID-19.	Major
6. Reside in the study health area for at least 6 months	Minor

Exclusion Criteria (CASES AND WITNESSES)

1. The subject has a contraindication at venipuncture, determined by clinical judgment	Major
2. The subject is vaccinated against SARS- CoV-2	Major
3. The subject has been infected with SARS- CoV-2 in the past and now presents with a reinfection	Major

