7. ANALYSIS

A conditional logistic regression model will be fitted with the logarithm of malaria antibody levels to Circum Sporozoite Protein (CSP) as the independent variable. The p-value for the test of no association between malaria antibody levels and case/control will be presented.

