8. ANALYSIS SECONDARY

- Compare malaria antibody levels to other antigens between severe and non-severe COVID-19 cases:
 - A similar model to the one for the primary objective is fitted with the respective malaria antibody levels as the independent variable.
- Compare the cellular response against malaria between severe and non-severe COVID-19 cases:
 - A conditional logistic regression model will be fitted with the cellular response to malaria as the independent variable.
- Compare the proportions of acute malaria infection between severe and non-severe cases of COVID-19 using the Thick Gauge (TG) and Rapid Diagnostic Test (RDT):
 - A conditional logistic regression model will be fitted with acute malaria infection as the independent variable.

Note: Acute infection will be assessed in 3 ways: first with the EWG alone, then the RDT alone and finally the EWG or RDT taken together.

- Describe the clinical characteristics and clinical status of severe and non-severe cases of COVID-19 with and without malaria (former exposure or active infection):
 - Medians with quartiles or frequencies and proportions will be presented in 3 types of tables:
 - ▶ Cases versus controls
 - ▶ Malaria present versus malaria absent
 - ▶ Malaria cases present/absent versus Controls-Malaria present/absent

Statistical comparisons between groups (cases versus controls and malaria present versus absent) will be performed. The Fisher's exact statistical test or Chi-square test will be used to compare categorical clinical characteristics and the non-parametric Man-Whitney test for numerical characteristics.

- To assess the modulating impact of existing antimalarial immunity on the strength of humoral and cellular immune responses to SARS-COV-2 in severe and non-severe cases of COVID-19
 - The Spearman correlation between malaria immunity and immune responses to SARS-COV-2 will be calculated with a 95% confidence interval. separately for cases and controls
- Compare the SARS-COV-2 specific cellular immune response between severe and non-severe cases
 - A conditional logistic regression model will be fitted with the SARS-COV-2 specific cellular immune response as the independent variable
- Assessing the modulatory impact of antimalarial immunity on induced immunity using specific antiviral receptor stimulations of the innate immune system

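### Does recruiting a control up to 10 weeks after its case, with no analysis of calendar date, call for a change to the SAP?

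*SAP*

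**What the plan says.** SAP section 5.2 gives one control per case, matched on age within 10 years, gender and Health Zone, and then sets the window: "The time to recruit a control is up to 10 weeks after case recruitment". Protocol section 5.1.4 does not match on date either and sets no case-to-control limit. It takes "The first two controls on the linear list with a COVID-19 RT-PCR test result of 72 hours or less", and those 72 hours run from the control's own test, so they do not tie the control's date to the case's. Protocol section 5.2.1 adds that "Blood samples for cases and controls will be taken on D1 of the study", so the recruitment lag is also the lag between blood samples.

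The primary model in SAP section 7 has a single regressor: "A conditional logistic regression model will be fitted with the logarithm of malaria antibody levels to Circum Sporozoite Protein (CSP) as the independent variable". For acute malaria, SAP section 8 says "A conditional logistic regression model will be fitted with acute malaria infection as the independent variable". Nothing in SAP sections 7 to 9 uses date or lag.

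SAP section 6.2 states that "Only participants who did not violate any major criteria will be included in the secondary analysis". Its Table 1 covers eligibility only. It grades the 72-hour test window as major, but lists no case-to-control lag violation and no matching violation of any kind.

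Protocol section 7 said the SAP would cover "management of confounding factors and interactions), subgroup definitions and sensitivity analyses". SAP section 1 allows further work outside the plan: "Additional analyses may be performed but are not covered by the current analysis plan".

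**The concern.** On the plain reading a control is never sampled before its case. If malaria exposure rises or falls steadily over recruitment, the shift does not average out across pairs. It adds to the case-control difference, where it would be read as protection or harm in the primary test and in the acute malaria comparison.

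The usual repair is not available. The within-pair date difference never changes sign, so a linear or other monotone date term has no finite estimate in a 1:1 conditional logistic model. Someone who noticed a trend late would find that the obvious adjustment fails. The protocol had also said that the SAP would deal with confounding and sensitivity analyses, and the SAP has neither for this lag.

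**Working it through.** **Inputs from the documents.** Protocol section 5.1.5 gives SD 1 on the log scale in cases and controls, case-control correlation 0.7, a two-sided 5% test, a target log difference of 0.19 (6.8 against 6.61), and 100 cases with 200 controls. SAP section 5 gives one control per case. The protocol synopsis puts data collection in July to December 2021, which is 184/7 = 26.3 weeks.

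**Inputs assumed.** 100 pairs (the protocol's 100 cases at the SAP's 1:1 ratio, since the SAP states no number), a log-linear weekly drift, and a uniform lag with the mean shown below.

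**The protocol's own figure.** For 1:2 sets, also taking 0.7 between the two controls, the variance of case minus mean of controls is 1 + (1 + 0.7)/2 − 2 × 0.7 = 0.45. The SE is √(0.45/100) = 0.0671, and 0.19/0.0671 = 2.83. Power is Φ(2.83 − 1.96) = 0.81, as the protocol's table states. The set-up therefore reproduces the plan.

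**Effect of a trend in 1:1 pairs.** Bias = weekly drift × mean lag. SE = √(2(1 − 0.7)/100) = 0.0775. The chance of rejecting a true null is P(|N(bias/SE, 1)| > 1.96). The simulated column is a conditional logistic model with a Wald test, 20,000 runs; with no drift it gives 4.7% (mean lag 5 weeks) and 4.9% (mean lag 2 weeks).

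| Drift per week | Mean lag (weeks) | Bias | Bias/SE | Approximation | Simulated |
|---|---|---|---|---|---|
| 0.01 | 2 | 0.02 | 0.26 | 5.8% | 5.5% |
| 0.02 | 2 | 0.04 | 0.52 | 8.1% | 7.3% |
| 0.01 | 5 | 0.05 | 0.65 | 9.9% | 9.3% |
| 0.02 | 5 | 0.10 | 1.29 | 25.2% | 23.4% |

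**Sensitivity to the assumptions.**
- With correlation 0.3 the SE is √(1.4/100) = 0.118. The simulated rates fall to 6.3% and 12.4% (mean lag 5) and 4.5% and 5.9% (mean lag 2).
- With a right-skewed lag (exponential, mean 3 weeks, capped at 10), the rates are about 6% and 10% at correlation 0.7, and 5% and 7% at 0.3.
- A drift of 0.01 or 0.02 per week kept up for 26 weeks means a rise in median titre of exp(0.26) − 1 = 30% or exp(0.52) − 1 = 68%.
- A 0.02 trend that reverses at week 13 gives about 6% when cases enter over 16 or 26 weeks, but 22% when all enter in the first 6.
- To mimic the whole 0.19 at a mean lag of 5 weeks, drift must be 0.19/5 = 0.038 per week, or 3.9%.
- For acute malaria, assume starting positivity of 10% to 30%, mean lag 5 weeks, case entry over 16 weeks and a latent pair correlation of 0.3. A rise of 0.5 points per week gives 7% to 8%, and 1 point per week gives 12% to 17%, against 5% to 6% with no trend.

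**Date in the paired model.** With 100 pairs and date as the only covariate, the log-likelihood starts at −100 × ln 2 = −69.3. It rises to −2.0 at a coefficient of 10 and to almost 0 at 500, so there is no finite estimate.

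**What added checks could show.** These figures are simulated with 100 pairs, lag uniform over 0 to 10 weeks, 12 or 35 zones, case entry over 6 or 16 weeks, and correlation that is either all zone-driven or partly pair-specific.
- Regressing log anti-CSP on date among controls has a 95% half-width of 0.022 to 0.062 per week and power 0.10 to 0.45 for a drift of 0.02. Pooling cases and controls with a case indicator raises that power to about 0.15 to 0.60.
- Breaking the pairs and adjusting for calendar month within Health Zone has power 0.18 to 0.60 for 0.19, against 0.66 to 0.68 for the paired model. Its false-positive rate under a 0.02 drift runs from 2% to 7%. About 23 of 100 controls (16-week entry) or 43 of 100 (6-week entry) fall in months with no cases and add nothing.

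**The case for a change.** The best argument for amending the SAP is that the gap is real and cheap to fill. Protocol section 7 left confounding and sensitivity analyses to the SAP, which is silent here. The natural adjustment cannot be estimated, which favours choosing a workable one before the data are seen. The lag table alone would be informative: at a mean lag of 2 weeks the issue largely disappears, and at 5 weeks it may not. The cost is a table, a plot with a regression, and one supportive model per outcome, using Day 1 dates already held.

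The facts in that argument stand, and so does the value of the lag table as good reporting. The step to a required change does not. None of the additions alters the primary test. The date regression would often miss a drift of 0.02 per week, so a flat slope would not reassure. The pair-breaking model gives up the matching that the sample size relies on. A reader who could not tell drift from association before would often be unable to tell after.

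The higher error rates also need an unbroken trend, long lags and high correlation together. Ten weeks is a ceiling, and taking the first eligible people on a current list suggests many lags may be short, though it does not prove it. The malaria variation that the documents describe within Kinshasa is between urban and peri-urban areas, and Health Zone matching addresses that.

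**Conclusion.** No change to the plan. The omission is there in the text, but the documents show no calendar trend and so no wrong result from the plan as written. If there is a trend, the effect runs from negligible (about 5% to 8% false positives at a mean lag of 2 weeks) to material (9% to 25% at 5 weeks), for drifts of 0.01 to 0.02 log units per week. Those figures rest on the protocol's SD and correlation and on an assumed number of pairs, drift and uniform lag.

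The window is a fair trade-off. A case with no control adds nothing to a conditional likelihood, so allowing time to find one of the same zone, sex and age protects the sample, and the SAP's cap is tighter than the protocol's absence of one. Tabulating the lag and plotting log anti-CSP and malaria positivity by sampling date, with a pooled regression on date, is something the analysts can sensibly add under SAP section 1. They should say that a flat slope does not rule out bias. A model that breaks the pairs is optional at most.
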